Purpose of clinical trial	
The purpose of this study is to assess accuracy and reliability of the HEKcite therapeutic drug monitoring device and compare these results with blood samples acquired at predetermined time points in kidney transplantation patients.
 
To date, only static data via blood samples is available, and too many grafts are rejected because of lack of dynamic measurements. This HEKcite biosensor provides a dynamic measurement device

	
which will improve drug compliance and the knowledge about receptor occupancy of therapeutic drugs in humans, and will eventually lead to fewer graft rejections, and thus better overall survival rates.

Primary objective	
Assessment of the accuracy and reliability of the monitoring device compared to reference standard of care blood values.

Secondary objective (s)	
To evaluate the mechanical stability of the HEKcite device To evaluate the biological stability of the HEKcite device after 6 months To evaluate the impact of the HEKcite device on drug compliance To evaluate the impact of the HEKcite device on graft functionality To evaluate the impact of the HEKcite device on patient' quality of life, assessed through KDQOL To evaluate the impact

Trial Design	
Open-label, interventional trial

Endpoints	
Graft survival [Time frame: 24 months] Urinalysis and GFR determination [Time frame: 24 months] Effects of immunosuppression weaning procedure on immunosuppression-related side effects (diabetes, hypertension, nephrotoxicity, hyperlipidemia) [Time frame: 24 months]

Sample Size	
50

Summary of eligibility criteria	
18 years to 75 years (adult, senior) Both sexes, no healthy volunteers

IMP, dosage and route of administration	Immunosuppressants, normal dosage, standard of care
Active comparator product(s)	None
Maximum duration of treatment of a Subject	24 months
Version and date of final protocol	20/09/2017
Version and date of protocol amendments	x

2. Background and rationale

3. Trial objectives and Design

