3.1 Trial objectives

We aim to demonstrate the added value of the of the HEKcite therapeutic drug monitoring device and compare these results with blood samples acquired at predetermined time points in kidney transplantation patients. Accuracy and reliability of the monitoring device will be assessed by comparison to reference blood values.

Postop quality of life will be assessed using a KDQOL. Patient will fill a pre-printed form with the KDQOL at the day of surgery, and at every study visit. Patients will also reports the time and the dose of analgesics they are taking post operatively to control pain in that form. Patients will submit all the data to the surgeons at all follow-up appointments.

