3.3 Secondary endpoints

- Quality of life
- Urinalysis and GFR determination [Time frame: 24 months]
- Assessment of PK/PD data of immunosuppressants level in plasma [Time frame: 24 months]
- Assessment of influence of outside temperature on sensitivity and efficacy of HEKcite device [Time frame: 24 months]
- Effects of immunosuppression weaning procedure on immunosuppression-related side effects (diabetes, hypertension, nephrotoxicity, hyperlipidemia) [Time frame: 24 months]

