3.4 Trial Design

An prospective, monocenter, open label, one-arm, interventional trial to assess the safety and efficacy of the HEKcite therapeutic drug monitoring device is proposed.

flowchart of routine practice is presented in figure 1.

At time of first presentation at the University Hospital of Leuven, campus Gasthuisberg, more specifically at the department of nephrology (E409), a thorough clinical examination with urinalysis and a blood sample to examine the GFR value, is performed to confirm the diagnosis of end stage kidney disease (GFR < 15 ml/min/1.73 m²). Next, patients are informed about their clinical condition and the proposed treatment plan. After patients have provided their written informed consent, a preoperative plan is prepared.

All patients will be treated by the local team of abdominal transplantation surgeons and nephrologists from the University Hospital of Leuven, campus Gasthuisberg. The principal investigator will be responsible for the training of all investigators, to ensure rehabilitation according to the protocol.

Operation plan

When determined if a patient is eligible for both transplantation surgery and placement of the HEKcite device in the forearm, the operative plan is assessed. Kidney transplantation surgery cannot always be planned in advance. If a kidney donor graft is easily accessible, dates and other important data are planned and if not, these are planned as soon as a kidney donor graft becomes accessible. As previously described, the choice of surgical technique is the responsibility of the surgeons.

The preferred forearm for the HEKcite device is determined, in accordance with the patient and the surgeon. Standard protocol is to implant in the right forearm, but patient preference will be considered, as well as certain criteria (amputation, nerve deterioration, ...) that make these standards impossible.

Placement of the HEKcite device by making a medio-lateral incision of approximately 1.5 cm. Next, the device is placed subcutaneously, ensuring neovascularization around and 'through' the device

itself. The device is expected to be encapsulated by fibrin fibers, ensuring safe preservation in the forearm.

Clinical evaluation

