9.2 Randomisation

No randomization needed.

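### The one-arm design cannot support the secondary objectives on the device's impact on compliance, graft function and quality of life, and the weaning endpoint refers to a procedure that the protocol does not describe

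*Protocol*

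**What the plan says.** **Objectives.** The protocol synopsis includes these secondary objectives: "To evaluate the impact of the HEKcite device on drug compliance To evaluate the impact of the HEKcite device on graft functionality". It continues with "To evaluate the impact of the HEKcite device on patient' quality of life, assessed through KDQOL". Section 3.1 opens with "We aim to demonstrate the added value" of the device and, in the same sentence, ties this to a comparison with blood samples.

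**Design.** Section 3.4 describes "An prospective, monocenter, open label, one-arm, interventional trial". Section 9.2 reads "No randomization needed", and the synopsis enters no active comparator. No historical control, external control or benchmark is named anywhere. The trial flowchart marks transplant surgery and device implantation in the same day 0 column. Section 3.1 has KDQOL completed on the day of surgery and at each study visit.

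**Analysis.** The Statistics section calls the analysis mainly descriptive. It applies a matched-pairs Wilcoxon test or a repeated-measures ANOVA to follow KDQOL and other parameters over time.

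**Weaning.** The synopsis and section 3.3 list as an endpoint "Effects of immunosuppression weaning procedure on immunosuppression-related side effects", naming diabetes, hypertension, nephrotoxicity and hyperlipidemia. The synopsis gives the medication as "Immunosuppressants, normal dosage, standard of care".

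**The concern.** Impact is a causal word. It needs an estimate of what compliance, graft function and quality of life would have been without the device, and this design provides none. Patients enter with end-stage disease (section 3.4 gives a GFR below 15 ml/min/1.73 m²). A working graft would be expected to change GFR and probably quality of life whether or not the device does anything. Compliance is no easier: section 5.2 excludes earlier transplant recipients, so adherence to a post-transplant regimen has no value from before the device.

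At stake is what the trial may conclude. A significant change in KDQOL or GFR after day 0 would fit the objective as worded, yet would carry no information about the device.

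The weaning endpoint is a separate difficulty. The effect of a procedure cannot be evaluated from a protocol that does not say what the procedure is, who undergoes it, or when.

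**Working it through.** **Step 1: is there a figure to reproduce?** No. Section 9.1 gives at least 40 patients, the synopsis 50, and section 3.7 50 to 60. No alpha, power, effect size, SD or dropout rate accompanies any of them. The point is about identification, so the arithmetic below is illustration only.

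**Step 2: what the data can estimate.** Let τ be the mean change due to the transplant, its aftercare and time, and δ the mean change due to the device. Both start on day 0 in every patient, so the within-patient comparison estimates only the sum:

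Δ = τ + δ

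An observed Δ of 0.5 SD fits (τ, δ) = (0.5, 0), (0.3, 0.2) or (0.8, −0.3) equally well. More patients estimate Δ more precisely but do not split it.

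**Step 3: size of the problem under stated assumptions.** Assumed, not in the protocol: δ = 0; τ = 0.3, 0.5 or 0.8 SD of the paired difference; normal differences; complete data; two-sided alpha 0.05. For a paired t test, the probability of significance is P(|T| > t₀.₉₇₅,ₙ₋₁), where T is noncentral t with n − 1 degrees of freedom and noncentrality τ√n. At n = 50 the noncentrality is 0.3 × 7.071 = 2.12, 0.5 × 7.071 = 3.54 and 0.8 × 7.071 = 5.66. The Wilcoxon column comes from 3000 simulated trials per cell.

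| n | assumed τ (SD) | paired t | Wilcoxon |
|---|---|---|---|
| 40 | 0.3 | 0.457 | 0.431 |
| 40 | 0.5 | 0.869 | 0.855 |
| 40 | 0.8 | 0.999 | 0.996 |
| 50 | 0.3 | 0.548 | 0.535 |
| 50 | 0.5 | 0.934 | 0.924 |
| 50 | 0.8 | 1.000 | 0.999 |
| 60 | 0.3 | 0.628 | 0.608 |
| 60 | 0.5 | 0.968 | 0.964 |
| 60 | 0.8 | 1.000 | 1.000 |

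A second Wilcoxon simulation at n = 50 with 4000 trials gave 0.514, 0.921 and 0.999. Taking all three sets, the ranges at n = 50 are about 51–55%, 92–93% and about 100%. With τ = 0 the rate stays near 0.05, as it should.

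**Step 4: would a control arm be feasible at this size?** Assume a 1:1 concurrent control, 80% power and two-sided alpha 0.05. Patients per arm = 2(1.960 + 0.842)²/d² = 15.70/d². This gives 175, 63 and 25 per arm for a device effect d of 0.3, 0.5 and 0.8 SD. Splitting 50 patients 25:25 gives power Φ(d√12.5 − 1.960) = 0.18, 0.42 and 0.81. Only a large effect could be studied, so rewording is the practical remedy.

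**Step 5: the weaning passages side by side.** The term occurs only in the two endpoint lists. The trial design, flowchart, procedures and efficacy sections contain no weaning step, schedule or comparison. The only statement on dosing is the synopsis entry quoted above. Nothing links the two.

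**The case against.** The strongest reply is that the protocol promises little inference. Its analysis is mainly descriptive, the tests are said to follow the course of quality of life, and no sentence says that a change will be credited to the device. That is fair. A reader might infer that any positive result will be misattributed, but this predicts how results will be reported, and the documents do not say it. What stands is narrower: such a result could not be attributed to the device, although the objectives ask for exactly that.

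Four further inferences also go too far.

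- **That added value cannot be shown at all.** The sentence in section 3.1 goes on to the comparison with blood samples. One arm can address that, since each patient supplies both readings.
- **That the trial contains no weaning.** The content of standard of care is not itemised, and Figure 1, captioned as routine practice, is not available in the text reviewed. The procedure is undescribed and unreconciled; it is not shown to be absent.
- **That the side effects will go unmeasured because the flowchart has no row for blood pressure, glucose or lipids.** KDQOL has no row either, yet sections 3.1 and 6.1 require it. Section 6.1 applies standard-of-care procedures, physical examination is scheduled at every visit, and GFR and urinalysis at least partly cover nephrotoxicity. A missing row does not show that values are not collected.
- **That the percentages are the chance of a false claim.** They are ordinary paired-test power under assumed shifts. They would become that chance only if every significant time trend were reported as a device effect.

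None of this supplies a comparator. A later SAP could refine the paired analysis, but it could not separate two interventions given on the same day to every patient.

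**Conclusion.** The point holds for the secondary objectives on compliance, graft function and KDQOL: the design identifies no device effect on any of them. This follows from the single arm, the shared day 0 and the within-patient analysis, and needs no numerical assumption. The 51–55%, 92–93% and roughly 100% at n = 50 only illustrate how often a device with no effect would accompany a significant change. They rest on assumed shifts, an assumed alpha and complete data. The protocol gives neither the size nor the direction of any expected KDQOL change, and at the smallest assumed shift significance is close to an even chance.

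The primary objective (accuracy and reliability against blood values) is untouched, as are implant stability and infection. These are within-device or descriptive questions.

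The weaning endpoint cannot be evaluated as written, because its procedure is not described and its relation to the dosing statement is left open.

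**What to change.** 1. **Synopsis, secondary objectives.** Replace the three impact objectives with: *describe compliance, graft function and KDQOL over 24 months in patients carrying the device*. The 24 months follows the synopsis, section 3.7 and the flowchart. Section 5.6 gives one year for quality of life, so the wording should match whichever follow-up is settled.
2. **Section 3.1.** Limit added value to the comparison of device readings with blood values.
3. **Both places.** State that no effect of the device on compliance, graft function or quality of life will be claimed.
4. **Weaning endpoint (synopsis and section 3.3).** Reconcile it with the synopsis's dosing statement. If no weaning procedure is part of the trial, restate the endpoint as the incidence of the listed immunosuppression-related side effects, taken from routinely collected values.

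**Cost.** Items 1 to 3 are wording, and the downside is a less ambitious claim. Item 4 needs a decision by the sponsor and, if the endpoint is restated, transcription of routine values to the CRF.

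**Limit of the fix.** Section 5.4 withdraws and replaces patients for poor compliance or graft rejection, keeping their data up to that point. Even a descriptive summary will therefore have shortened follow-up in patients with the worst outcomes, and rewording does not remove this. Withdrawals and their reasons should be reported beside the summaries.

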3.1 Trial objectives

We aim to demonstrate the added value of the of the HEKcite therapeutic drug monitoring device and compare these results with blood samples acquired at predetermined time points in kidney transplantation patients. Accuracy and reliability of the monitoring device will be assessed by comparison to reference blood values.

Postop quality of life will be assessed using a KDQOL. Patient will fill a pre-printed form with the KDQOL at the day of surgery, and at every study visit. Patients will also reports the time and the dose of analgesics they are taking post operatively to control pain in that form. Patients will submit all the data to the surgeons at all follow-up appointments.

3.2 Primary endpoints

Graft survival [Time frame: 24 months]

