8.3 Treatment stopping rules

8.4 Data monitoring committee (DMC)

Some indications for setting up a data monitoring committee:

- Life-threatening disease
- Patient population (e.g. pediatric population)
- Prior knowledge or strong suspicion that a treatment under consideration has the potential to harm patients
- Complex study design

For further information:

http://www.emea.europa.eu/docs/en_GB/document_library/Scientific_guideline/2009/09/WC500003635.pdf

8. Statistics

Wilcoxon-matched pairs test or repeated measures ANOVA will be applied to examine the evolution of QOL, assessed with the kidney disease quality of life (KDQOL), at respectively the two and three time-points for analysis of the primary endpoint hypothesis.

Statistical analysis will primarily consist of descriptive analysis. Wilcoxon-matched pairs test or repeated measures ANOVA will be applied to examine the evolution of different parameters at several time points. Regression analysis will be performed to examine the influence of different variables on biological and mechanical stability. All analysis will be performed using Prism® software (GraphPad Prism 5, Inc., La Jolla, CA) and SPSS software (version 21, IBM SPSS statistics, Chicago, IL).

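### The primary objective (device accuracy), the only primary endpoint (24-month graft survival) and the analysis labelled primary (KDQOL change) are three different outcomes, and no endpoint captures device-versus-blood agreement

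*Protocol*

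**What the plan says.** The synopsis states the primary objective as "Assessment of the accuracy and reliability of the monitoring device compared to reference standard of care blood values". Section 3.1 repeats it: "Accuracy and reliability of the monitoring device will be assessed by comparison to reference blood values".

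Section 3.2 has one entry, "Graft survival [Time frame: 24 months". The synopsis endpoint list also opens with graft survival.

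The Statistics section (headed 8, after 8.4) applies a Wilcoxon matched-pairs test or repeated measures ANOVA "to examine the evolution of QOL, assessed with the kidney disease quality of life (KDQOL), at respectively the two and three time-points", and describes this as being "for analysis of the primary endpoint hypothesis". Yet "Quality of life" is the first bullet under the secondary endpoints in section 3.3, and the synopsis places "quality of life, assessed through KDQOL" among the secondary objectives.

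The Assessment of efficacy section (headed 6, after 6.2) says the blood concentrations will be compared with what the device's application reports. It gives no measure of agreement and no acceptance limit, and ties the comparison to no endpoint.

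**The concern.** The primary endpoint should measure what the primary objective asks, and the primary analysis should analyse that endpoint. Here each of the three names something else.

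Graft survival in a one-arm study does not show whether a sensor reads correctly, and neither does a change in quality of life. Followed literally, the protocol would headline a graft-survival percentage or a KDQOL p-value. The comparison for which the device is being implanted would have no endpoint status and no criterion for success or failure. The stated sample sizes are also tied to none of the three outcomes, so a reader cannot tell what the trial was sized to show.

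**Working it through.** **Step 1. The statements side by side**

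| Element | Where | Outcome named |
|---|---|---|
| Primary objective | Synopsis; section 3.1 | Device accuracy and reliability against blood values |
| Primary endpoint | Section 3.2 | Graft survival at 24 months |
| Analysis labelled primary | Statistics section | Change in KDQOL |
| Status of quality of life | Synopsis; section 3.3 | Secondary |
| Planned device-versus-blood comparison | Section 3.1; Assessment of efficacy | Agreement, without metric or limit |

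The two listed endpoints nearest to the objective are both secondary in section 3.3. One is immunosuppressant PK/PD in plasma, which is the reference side only. The other is the influence of outside temperature on device sensitivity and efficacy. Neither is agreement between device and blood. The remaining analyses in the Statistics section are descriptive summaries, tests of change over time, and regression for device stability. No agreement method and no survival method is named.

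**Step 2. Data that could bear on accuracy**

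The trial flowchart marks PK/PD blood samples at Day 1, Week 1, Week 6 and Months 6, 12 and 24, which is six post-implant draws. The screening sample precedes implantation, and none is marked on day 0. At 50 patients that is 50 × 6 = 300 nominal pairs. This is a ceiling before withdrawals, and it needs a device reading at every draw. The six pairs from one patient are correlated, so they are not 300 independent observations.

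**Step 3. What the stated primary endpoint would deliver**

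The stated sample sizes are at least 40 (section 9.1), 50 (synopsis) and 50 to 60 (sections 3.7 and 5.6). None has a derivation, so there is no figure to reproduce. The protocol gives no survival rate, so 85%, 90% and 95% are assumptions. The exact (Clopper-Pearson) 95% limits for x surviving grafts out of n are the 2.5% point of Beta(x, n−x+1) and the 97.5% point of Beta(x+1, n−x), with x rounded to a whole number:

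| n | about 85% | 90% | about 95% |
|---|---|---|---|
| 40 | 34/40: 70.2–94.3% | 36/40: 76.3–97.2% | 38/40: 83.1–99.4% |
| 50 | 42/50: 70.9–92.8% | 45/50: 78.2–96.7% | 48/50: 86.3–99.5% |
| 60 | 51/60: 73.4–92.9% | 54/60: 79.5–96.2% | 57/60: 86.1–99.0% |

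The design is one-arm, the synopsis lists no active comparator, and no performance goal is stated. There is nothing to set any of these intervals against.

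**Step 4. The three outcomes imply three different sizing criteria**

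These figures are illustrative, for n = 40 / 50 / 60:

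- Agreement, one pair per patient, in units of the SD of the differences. The 95% half-width for each limit of agreement is about 1.96 × √(3/n) = 0.54 / 0.48 / 0.44. For mean bias it is 1.96/√n = 0.31 / 0.28 / 0.25.
- KDQOL paired change, assuming two-sided 5% and 80% power. The detectable standardised change is (1.96 + 0.84)/√n = 0.44 / 0.40 / 0.36.
- Graft survival: the interval widths in Step 3.

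The protocol commits to none of these.

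**The case against.** The strongest reply is that the accuracy comparison is planned. Section 3.1 and the Assessment of efficacy section both say so, and the blood draws are on the flowchart. That stands. A reader might infer that the trial cannot answer its primary question at all, but the documents do not support that. Paired data could be collected. What is missing is an endpoint and a named analysis that use them.

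Second, section 3.2 names only one primary endpoint, and the KDQOL clause may simply be a labelling error. That is fair. A reader might infer that the protocol leaves three rival primaries open for choice after the data are seen. The documents show contradictory labels, not an intention to choose among them. The clause still needs correcting, because it conflicts with both the synopsis and section 3.3.

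Third, graft survival is not foreign to the aims. Section 3.1 speaks of added value, and the synopsis expects fewer rejections. This is a reason to keep it as an outcome. It does not make it a measure of accuracy, and a one-arm design with no benchmark cannot show that the device improves it.

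Fourth, a statistical analysis plan may exist and may specify agreement statistics. It could supply the detail, but it cannot settle which of three conflicting protocol statements governs.

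Finally, the remedy must not assume that the device reports a concentration. The protocol speaks only of information from the application, and the synopsis also mentions receptor occupancy. It does not say when readings begin. This limits what the fix can specify.

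**Conclusion.** The contradiction is in the current text and rests on no assumption: accuracy is the objective, 24-month graft survival is the sole primary endpoint, and KDQOL change carries the primary-analysis label. A device-versus-blood comparison is intended, but no primary or secondary endpoint and no named analysis captures it. This should be corrected before the trial proceeds, because the primary endpoint determines the sample size, the analysis and the main claim.

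On size, across assumed survival of 85% to 95% and 40 to 60 patients, the stated primary endpoint gives exact intervals from about 70–94% to 86–99% with no yardstick. The survival rates are assumptions; the lack of a yardstick is not.

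Two further inferences go too far. The 300 scheduled pairs at 50 patients are a nominal maximum of clustered readings, not a sample size for accuracy. Nor can the present enrolment be called adequate for an agreement endpoint, since no acceptance limit or SD is given.

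**What to change.** - **Synopsis endpoints, section 3.2 and the Statistics section:** make device-versus-blood agreement at the six scheduled post-implant draws the primary endpoint. If the device reports a concentration, use mean bias and 95% limits of agreement, with confidence intervals, from a method that allows for repeated measures within patient, judged against an acceptance limit set in advance. If it reports something else, prespecify an agreement measure suited to that output.
- **Section 3.3:** list 24-month graft survival as a descriptive outcome. Section 5.4 withdraws and replaces patients with graft rejection, so state that graft losses in withdrawn patients are counted.
- **Statistics section:** delete "for analysis of the primary endpoint hypothesis" from the KDQOL sentence, so that quality of life stays secondary there as it is elsewhere.
- **Section 9.1:** state the precision that the planned sample size gives for the agreement endpoint, and reconcile the figures of 40, 50 and 50 to 60.

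The cost is a protocol amendment to these sections. The blood draws are already scheduled, so no new draw is needed for this endpoint. Whether more patients are needed cannot be said until the acceptance limit is set.
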